Secukinumab may increase the risk of infections. In clinical trials, a higher rate of infections was observed in secukinumab-treated subjects compared to placebo-treated subjects. In placebo-controlled clinical trials, higher rates of common infections such as nasopharyngitis (11.4% versus 8.6%), upper respiratory tract infection (2.5% versus 0.7%) and mucocutaneous infections with candida (1.2% versus 0.3%) were observed with secukinumab compared with placebo. The incidence of some types of infections appeared to be dose-dependent in clinical studies. Proper exclusion criteria will be applied in this study to ensure subject safety.

Pre-treatment evaluation of tuberculosis

Evaluate subjects for tuberculosis (TB) infection prior to initiating treatment with secukinumab. Do not administer secukinumab to subjects with active TB infection. Initiate treatment of latent TB prior to administering secukinumab. Consider anti-TB therapy prior to initiation of secukinumab in subjects with a past history of latent or active TB in whom an adequate course of treatment cannot be confirmed. Subjects receiving secukinumab should be monitored closely for signs and symptoms of active TB during and after treatment.

Inflammatory Bowel Disease

Caution should be used when prescribing secukinumab to patients with inflammatory bowel disease. Exacerbations, in some cases serious, occurred in secukinumab treated patients during clinical trials in plaque psoriasis, psoriatic arthritis and ankylosing spondylitis. In addition, new onset inflammatory bowel disease cases occurred in clinical trials with secukinumab. In an exploratory study in 59 patients with active Crohn's disease, there were trends toward greater disease activity and increased adverse events in the secukinumab group as compared to the placebo group. Patients who are treated with secukinumab should be monitored for signs and symptoms of inflammatory bowel disease.

Hypersensitivity reactions

Anaphylaxis and cases of urticaria occurred in secukinumab-treated subjects in the clinical trials. If an anaphylactic or other serious allergic reaction occurs, administration of secukinumab should be discontinued immediately and appropriate therapy initiated.

Risk of Hypersensitivity in Latex-sensitive Individuals

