14. Total white blood cell (WBC) count $< 2,500/\mu\text{l}$, or thrombocytes $< 100,000/\mu\text{l}$, or neutrophils $< 1,500/\mu\text{l}$, or hemoglobin < 8.5 g/dL at screening
15. History of lymphoproliferative disease or any known malignancy or history of malignancy of any organ system within the past 5 years (except for skin Bowen's disease, squamous cell carcinoma, basal cell carcinoma, actinic keratoses that have been treated, carcinoma *in situ* of the cervix, or non-invasive malignant colon polyps that have been removed)
16. History of an ongoing, chronic or recurrent infectious disease, or evidence of tuberculosis infection as defined by a positive or indeterminate QuantiFERON TB-Gold test (QFT) at screening. Subjects with a positive QFT test may participate in the study if a full tuberculosis work up (according to local practice/guidelines) completed within 12 weeks prior to randomization establishes conclusively that the subject has no evidence of active tuberculosis. If the presence of latent tuberculosis is established, then treatment must have been initiated and maintained for at least 4 weeks prior to randomization and the course of prophylaxis is planned to be completed
17. Positive serology for human immunodeficiency virus (HIV), hepatitis B or C infection, or known history of other severe, recurrent or persistent infections
18. Any underlying condition (including, but not limited to metabolic, hematologic, renal, hepatic, pulmonary, neurologic, endocrine, cardiac, infectious or gastrointestinal) which, in the opinion of the Investigator, significantly immunocompromises the subject and/or places the subject at unacceptable risk for receiving an immunomodulatory therapy
19. Active systemic infections during the 2 weeks prior to randomization (exception: common cold) or any infection that reoccurs on a regular basis
20. Plans for administration of live vaccines during the study period or 6 weeks before randomization
21. Any medical or psychiatric condition which, in the Investigator's opinion, would preclude the subject from adhering to the protocol or completing the study per protocol
22. History or evidence of ongoing substance abuse within 12 months prior to screening, or not willing to limit alcohol use to ≤ 14 drinks per week within 4 weeks prior to Baseline and throughout the duration of the study

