5.5.14 Early study termination

The study can be terminated at any time for any reason by Novartis. Should this be necessary, the subject should be seen as soon as possible and treated as a prematurely withdrawn subject (as described in [Section 5.5.9](#)). The Investigator may be informed of additional procedures to be followed in order to ensure that adequate consideration is given to the protection of the subject's interests. The Investigator will be responsible for informing the Institutional Review Board/Independent Ethics Committee (IRBs/IECs) of the early termination of the trial.

6 Visit schedule and assessments

[Table 6-1](#) lists all of the assessments and indicates with an "X" when the assessments are to be performed.

Subjects should be seen for all visits on the designated day or as close as possible to the original planned visit schedule (recommended visit windows are in [Table 6-1](#). Every effort should be made to respect the time frame for the Visit 8/Week 12 visit.

At a minimum, subjects will be contacted for safety evaluations during the 30 days following the last study visit, including a final contact at the 30-day point. Documentation of attempts to contact the subject should be recorded in the source documentation.

Visit windows

A "visit window" will be allowed during the study as follows:

- Screening Period
 - +2 days (for a total of up to 30 days)
- Double-blind Treatment Period
 - ± 2 days for Visits 3-8
- Open-label Treatment Period
 - ± 7 days for Visits 9-14

Rescreening

Rescreening may be allowed under certain conditions. Requests from the Investigator/site staff to rescreen subjects will be handled on a case-by-case basis with Medical Monitor approval required before proceeding with the rescreening. Rescreening cannot be done if a subject was previously randomized into the study.

If a subject rescreens for the study, the subject must sign a new ICF and be issued a new subject number. The date of the new informed consent signature should correspond to the new subject number. Informed consent for a rescreened subject must be obtained prior to performing study-related assessments or collecting any data for the Screening Visit. For rescreening, all

screening assessments must be performed as per protocol, except for the tuberculosis (TB) work up, if applicable, if performed not more than 12 weeks before randomization.

[figure not shown]

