6.2.8 Determination of tuberculosis status

Determination of tuberculosis (TB) status will be required before administration of study treatment. TB status must be determined by medical history, signs, symptoms, and TB testing (QuantiFERON-TB Gold assay). Any significant findings will be recorded in the appropriate eCRF(s), as necessary.

If the QuantiFERON-TB Gold Assay test is positive or indeterminate, a TB workup should be performed as defined by local guidelines to determine the subject's TB status.

QuantiFERON TB-Gold In-Tube assay

A QuantiFERON® TB-Gold In-Tube assay will be performed to assess the TB status at screening for all subjects. This test will only be used to determine subject's eligibility for the trial. The test will be used to screen the subject population for latent tuberculosis infection (Doherty, Van Vorhees and Lebwohl | 2008).

This blood-based assay is specific for Mycobacterium tuberculosis and is not influenced by previous Bacillus Calmette-Guérin vaccination or exposure to other Mycobacteria species.

This test, in contrast to the purified protein derivative (PPD) skin test, is also insensitive to a booster effect since the subject is not exposed to the vaccine. The assay measures the production of interferon-gamma and presents it relative to a negative and a positive control sample (Manuel and Kumar 2008).

The QuantiFERON®-TB Gold assay test will be supplied by the central laboratory. Details on the collection, shipment of samples and reporting of results by the central laboratory are provided in the Laboratory Manual.

The results of a TB workup for a subject with a positive or indeterminate test must be recorded in the eCRF.

- If the test result is **negative**, the subject may be randomized
- If the test result is **positive**, the Investigator should perform a TB workup for the test result as per local procedures.
 - Subjects **positive** for latent TB per workup may be randomized to the trial if sufficient treatment has been initiated according to local routine clinical practice and will be maintained for the prescribed duration.
 - Subjects **positive** for active TB per workup are not eligible for the study.
 - Subjects **negative** for TB (no signs of latent or active TB) per workup may be randomized to the trial.

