- If the test result is **indeterminate**, it is **recommended to repeat the test once**. The Investigator may decide to skip the repetition of the test and proceed directly to the workup (however this is not recommended). If a TB workup was conducted prior to screening, results from the workup can be used to assess eligibility if the workup was conducted within 12 weeks prior to randomization.
 - If the second test is negative, the subject may be randomized.
 - If the second test is positive or indeterminate, the Investigator should perform a TB workup as per local guidelines. The subject will not be eligible for randomization if: “active tuberculosis is present”, or if “latent tuberculosis is present” and is untreated as per local guidelines.

Refer to Section 13 (Appendix 2) to see a schematic of the tuberculosis screening process and subject eligibility with respect to TB testing.

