13.2 Appendix 2: Tuberculosis screening flowchart

The subject will not be eligible for randomization if "active tuberculosis is present "or if "latent tuberculosis is present and is untreated as per local guidelines."

* If the first QuantiFERON® TB-Gold In-Tube test (QFT) is indeterminate, the investigator may choose to perform a second QFT or refer the subject for tuberculosis workup per local guidelines.

** If the result of any QFT is "positive" or the results of 2 sequential QFTs are "indeterminate", the subject must be referred to have a tuberculosis workup per local guidelines (if no workup within 12 weeks prior to randomization is available).

13.3 Appendix 3: Psoriasis Area and Severity Index (PASI) and Body Surface Area (BSA)

Body Region	Erythema (E)	Thickening (I) (plaque elevation, induration)	Scaling (D) (desquamation)	True Area % (covered by lesions)
Head and Neck (H)	 None (0)  Slight (1)  Moderate (2)  Severe (3)  Very severe (4)	 None (0)  Slight (1)  Moderate (2)  Severe (3)  Very severe (4)	 None (0)  Slight (1)  Moderate (2)  Severe (3)  Very severe (4)	Record % (0-100) _____ %
Trunk, Axillae and Groin (T)	 None (0)  Slight (1)  Moderate (2)  Severe (3)  Very severe (4)	 None (0)  Slight (1)  Moderate (2)  Severe (3)  Very severe (4)	 None (0)  Slight (1)  Moderate (2)  Severe (3)  Very severe (4)	Record % (0-100) _____ %

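### Exclusion criterion 16 and Section 6.2.8 give opposite answers for a subject with fewer than 4 weeks of latent tuberculosis treatment, and the protocol does not say which prevails.

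*Protocol*

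**What the plan says.** Two protocol texts state when a subject with latent tuberculosis may enter.

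- Section 4.2, exclusion criterion 16: once latent tuberculosis is established, "treatment must have been initiated and maintained for at least 4 weeks prior to randomization", and there must be a plan to complete the course.
- Section 6.2.8, positive-test branch: a subject with latent tuberculosis at work-up "may be randomized to the trial if sufficient treatment has been initiated according to local routine clinical practice", with the further condition that treatment will continue for its prescribed length. No minimum time before randomisation is given.

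Three other texts state when a subject may not enter. The indeterminate-test branch of Section 6.2.8 bars latent tuberculosis that is present "and is untreated as per local guidelines". Table 6-1 footnote H and the notes under Appendix 2 bar a subject if "latent tuberculosis is present and is untreated as per local guidelines". None of the three repeats the 4-week minimum. The Risks and benefits text in Section 3.6 says "Initiate treatment of latent TB prior to administering secukinumab", also without a minimum.

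Section 4.2 opens by making any subject who meets an exclusion criterion ineligible. Section 5.3 has the site contact the randomisation system only after all criteria are confirmed. Section 6.2.8 ends by pointing sites to Appendix 2 for eligibility in relation to tuberculosis testing.

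**The concern.** Tuberculosis status is a pre-treatment safety check for an immunomodulator, and Section 3.6 treats it as one. If two sections of the same protocol answer differently for the same subject, the roughly 10 sites can reach different decisions, depending on which page they work from. Section 6.2.8 is the operational text, set out test result by test result, and it gives an express permission without the 4-week condition. A site that follows it in good faith may randomise a subject whom criterion 16 excludes. That would be an eligibility deviation produced by the protocol's own wording.

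The SAP does not settle the matter. Its deviation EXCL16 (Table 5.1) refers only to a time specified in the protocol, without saying what that time is.

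**Working it through.** There is no statistical figure to reproduce. The check compares the rules for one subject and adds a short timing calculation.

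**Step 1. Same subject, each rule.** The minimum in criterion 16 is 4 × 7 = 28 days. Let d be the days of latent tuberculosis treatment completed at randomisation.

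| d | 4.2, criterion 16 | 6.2.8, positive-test branch | 6.2.8 indeterminate branch, footnote H, Appendix 2 notes |
|---|---|---|---|
| 0 (untreated) | excluded | not permitted | excluded |
| 1 to 27, sufficient by local practice | excluded | may be randomised | not excluded by these texts |
| 28 or more, sufficient by local practice, course to be completed | may participate | may be randomised | not excluded by these texts |

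The direct conflict is the middle row, between the first two rule columns. The last column shows silence on the 4 weeks, not a contrary permission.

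**Step 2. Does any text rank the rules?** Section 5.3 requires all criteria to be confirmed, which includes number 16. Section 6.2.8 does not refer back to 4.2, and 4.2 does not refer forward to 6.2.8. No section says which tuberculosis text governs.

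**Step 3. Timing for a subject first diagnosed at screening.**

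- Sections 3.1.1 and 3.1.1.1: Baseline no later than 28 days after screening starts. Slack = 28 − 28 = 0 days.
- Section 6, Visit windows: 2 further days, 30 in total. Slack = 30 − 28 = 2 days.

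Those 0 to 2 days must hold the central-laboratory result, the work-up and the start of treatment. The count runs to the Baseline visit. Sections 3.1.1.1 and 3.1.2 allow randomisation up to 7 days after the Baseline scan, and 3.1.1.1 ties that allowance to scans with clinically important findings. At the outside this gives 30 + 7 − 28 = 9 days, but it is not provided for tuberculosis treatment.

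**Step 4. Timing with rescreening.** Section 6 allows rescreening case by case with Medical Monitor approval. The work-up need not be repeated if done not more than 12 weeks before randomisation, although the QuantiFERON test must be. Here 12 × 7 = 84 days, and 84 − 28 = 56 days remain if treatment starts when the work-up is completed. The 4 weeks can therefore be met by this route, but the rescreening text does not mention the condition.

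**The case against.** The strongest reply is that the protocol can be read as one set of cumulative conditions. A negative test in the same list of 6.2.8 also leads to a statement that the subject may be randomised, and nobody would take that to waive the other criteria. With Sections 4.2 and 5.3 requiring every criterion to be checked, and Section 5.5.4 repeating this before the first dose, a site that follows the randomisation step must apply criterion 16.

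This stands in part. It gives a careful site a route to the 4 weeks. It does not remove the conflict, because the latent tuberculosis sentence in 6.2.8 addresses the very condition that criterion 16 regulates and states a different test for it. Section 6.2.8 then sends the site to Appendix 2, whose visible notes do not give the 4 weeks either.

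A reader might infer more than the documents support:

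- *That footnote H, the indeterminate branch and Appendix 2 also contradict criterion 16.* They are exclusions. Barring untreated latent tuberculosis does not admit everyone else, and a stricter exclusion can stand beside it. The Appendix 2 diagram is not available here, so only its notes can be judged.
- *That 6.2.8 admits anyone whose treatment has merely begun, or even an untreated subject.* It asks for treatment that is sufficient by local practice and will be continued. An untreated subject is not admitted by any of these texts.
- *That criterion 16 cannot be met by a subject tested at screening.* The single screening window is very tight, but rescreening exists and carries over the work-up. Criterion 16 also does not require treatment to begin during screening.

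**Conclusion.** The inconsistency is real and narrow. It lies between criterion 16 and one sentence of Section 6.2.8, and it affects subjects with 1 to 27 days of treatment that local practice regards as sufficient. How many of the approximately 84 subjects this would involve cannot be derived from the documents, and it may be few.

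The consequences are for consistent eligibility decisions on a safety-relevant rule and for the classification of deviations. It would be wrong to infer any effect on the trial's statistics: SAP Table 5.1 gives EXCL16 code 0, so no subject leaves an analysis set on this ground, and the sample size and primary analysis do not depend on it.

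The timing point is secondary. It assumes that latent tuberculosis is first found at screening and that treatment starts only then. On that assumption the slack is 0 to 2 days to the Baseline visit, and rescreening would be needed in practice. The correction should be made because it is cheap and concerns a safety check.

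**What to change.** Reconcile Section 4.2 criterion 16, Section 6.2.8, Table 6-1 footnote H and Appendix 2 (diagram and notes) so that all four state one latent tuberculosis rule, or so that three of them refer to the one that states it. Which rule applies is a clinical decision for the sponsor and is not judged here. If the agreed rule includes a minimum treatment time, add a cross-reference to the rescreening provision in Section 6 and say there how the condition is to be met. Then align the wording of SAP deviation EXCL16 with the agreed rule, so that the deviation can be identified consistently.

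The cost is a wording change through the amendment procedure of Section 11.1, a one-line edit to the SAP, and notice to sites. Sample size, visit schedule and analyses need not change for this purpose.

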5.1 Protocol requested treatment

5.1.1 Study treatment

The following study treatments will be used:

- **Study drug**
 - Secukinumab 150 mg; 1 ml liquid formulation in a single-use prefilled syringe (PFS)
- **Control drug**
 - Placebo to secukinumab 150 mg; 1 ml liquid formulation in a single-use prefilled syringe (PFS)

Study drug: secukinumab 300 mg

Secukinumab for subcutaneous (s.c.) injection is provided in a prefilled syringe (PFS) containing 150 mg secukinumab. Each secukinumab 300 mg dose is given as two s.c. injections of 150 mg.

Control drug: placebo

Placebo to secukinumab 150 mg for s.c. injection is provided in a matching prefilled syringe (PFS). Each PFS contains a mixture of inactive excipients, matching the composition of the secukinumab 150 mg dose. Each placebo dose is given as two s.c. injections of placebo to secukinumab 150 mg.

Secukinumab 150 mg prefilled syringes and placebo prefilled syringes will be supplied by Novartis.

All study treatments will be labeled appropriately.

5.1.2 Additional study treatment

No additional treatment beyond study treatment is requested for this trial.

5.2 Treatment groups

At Visit 2/Baseline, eligible subjects will be randomized to one of the following two treatment groups in a ratio of 1:1, with approximately 42 subjects per group:

1. **Secukinumab group:** Subjects (or trained caregivers) will self-administer (or administer to the subject) a dose of secukinumab 300 mg s.c. (two injections of the 150 mg prefilled

syringes) once weekly for five weeks (at Randomization, Weeks 1, 2, 3, and 4), followed by dosing every four weeks, starting at Week 8 through Week 48. In order to maintain the blinding during the Double-blind Induction Period, placebo s.c. doses (two injections of the placebo to 150 mg prefilled syringe) will be self-administered by the subjects (or trained caregivers) at Weeks 13, 14 and 15.

2. **Placebo group:** Subjects (or trained caregivers) will self-administer (or administer to the subject) a dose of placebo s.c. (two injections of the placebo prefilled syringes) once weekly for five weeks (at Randomization, Weeks 1, 2, 3, and 4), followed by a dose after four weeks at Week 8.

Beginning at Week 12, all subjects in the placebo group will be switched to treatment with secukinumab 300 mg s.c. Subjects will receive a dose of secukinumab 300 mg s.c. once weekly for five weeks (at Weeks 12, 13, 14, 15, and 16) followed by dosing every four weeks, starting at Week 20 through Week 48.

All subjects who enter the Double-blind Induction Period will self-administer the Week 12 dose following the completion of all assessments scheduled to be performed at Visit 8/Week 12 (Table 6-1).

The treatment groups and dosing frequency are also described in Table 5-1 below.

Table 5-1 Overview of study treatment

Treatment group	DB Treatment Period (Rand – Wk 12 pre-dose)	DB Induction Period (Wk 12 – Wk 15)	OL Treatment Period (Wk 16 – Wk 52)
Secukinumab 300 mg	2x s.c. secukinumab 150 mg injection at Rand, Wks 1, 2, 3, 4 and 8	2x s.c. secukinumab 150 mg injection at Wk 12 2x s.c. secukinumab 150 mg PBO injection at Wks 13, 14 and 15	2x s.c. secukinumab 150 mg injection at Wks 16 - 48
Placebo (PBO)	2x s.c. secukinumab 150 mg PBO injection at Rand, Wks 1, 2, 3, 4 and 8	2x s.c. secukinumab 150 mg injection at Wks 12, 13, 14, and 15	2x s.c. secukinumab 150 mg injection at Wks 16 – 48

DB = Double-blind; OL = Open-label; Rand = Randomization; Wk = Week

5.3 Treatment Assignment, randomization

At Visit 2/Baseline, all eligible subjects will be randomized via Interactive Response Technology (IRT) to one of two treatment groups. The Investigator or his/her delegate will contact the IRT after confirming that the subject fulfills all the inclusion/exclusion criteria. The IRT will assign a randomization number to the subject, which will be used to link the subject to a treatment group and will specify a unique medication number for the first box of study treatment to be dispensed to the subject. The randomization number will not be communicated to the caller.

The randomization numbers will be generated using the following procedure to ensure that treatment assignment is unbiased and concealed from subjects and Investigators/site staff. A subject randomization list will be produced by the IRT provider using a validated system that automates the random assignment of subject numbers to randomization numbers. These randomization numbers are linked to the two different treatment groups, which in turn are linked to medication numbers. A separate medication list will be produced by or under the responsibility of Novartis Drug Supply Management (DSM) using a validated system that automates the random assignment of medication numbers to boxes containing the study treatments(s).

The randomization scheme for subjects will be reviewed and approved by a member of the Novartis Biostatistics Group.

